8.5.1. Safety Monitoring Rules for Liver Chemistry Tests

The following rules are adapted from the draft guidance for industry, "Drug-Induced Liver Injury: Premarketing Clinical Evaluation," issued by the U.S. Department of Health and Human Services, Food and Drug Administration, July 2009.

In the event of an ALT or AST measurement that is $> 3 \times$ ULN at any time during the Study (Treatment or Post-Treatment Period), the initial measurement(s) should be confirmed as described above. Additional, confirmatory measurements should also be performed if ALT or AST levels increase to $5 \times$ ULN.

Frequency of Repeat Measurements: Subjects with confirmed ALT or AST levels $> 3 \times$ ULN should have their liver chemistry tests (ALT, AST, ALP, international normalized ratio (INR) and total bilirubin) retested at least once-weekly until ALT and AST levels become $\leq 1.2 \times$ ULN.

Further Investigation into Liver Chemistry Elevations: For subjects with confirmed ALT or AST levels $> 3 \times$ ULN, the following evaluations should be performed:

1. Obtain a more detailed history of symptoms and prior and concurrent diseases
2. Obtain further history for concomitant drug use (including nonprescription medications, herbal and dietary supplement preparations), alcohol use, recreational drug use, and special diets
3. Obtain a history for exposure to environmental chemical agents and travel
4. Serology for viral hepatitis (HAV IgM, HBsAg, HCV antibody, Cytomegalovirus, IgM, and Epstein-Barr Virus antibody panel)
5. Serology for autoimmune hepatitis (e.g., antinuclear antibody [ANA])

Additional liver evaluations, including gastroenterology/hepatology consultations, hepatic computed tomography (CT) or magnetic resonance imaging (MRI) scans, may be performed at the discretion of the Investigator, in consultation with the Sponsor Medical Monitor. Repetition of the above evaluations should be considered if a subject's ALT and/or AST levels reach $5 \times$ ULN.

8.5.2. Safety Monitoring Rules for Potassium

In the event of a potassium measurement ≥ 5.5 mmol/L at any time during the study (Treatment or Post-Treatment Period), the initial measurement(s) should be confirmed. If the initial potassium measurement is confirmed to be ≥ 5.5 mmol/L study drug is to be held. An ECG evaluation should be performed if the value is confirmed and signs of hyperkalemia should be assessed (delayed conduction, heart block, arrhythmias). If new signs consistent with hyperkalemia are present, proceed to stopping rules. The patient will start oral hydration with 1-liter fluids not containing potassium to induce diuresis. Measure potassium frequently until documented to be < 5.5 mmol/L. Dosing with study drug may continue after a confirmed potassium measurement < 5.5 mmol/L with Investigator and Sponsor Medical Monitor or designee consultation.

8.5.3. Safety Monitoring Rules for Blood Pressure

1. In the event of a SBP \leq 100 mmHg a second measurement must be done within a 30-minute period. If the subject's SBP is \leq 100 mmHg within the 30-minute period, an additional BP measurement should be taken within 48 hours at the Study Center, regardless of whether the initial BP measurements were taken in clinic or at home. If the subject then experiences an additional SBP measurement \leq 100 mmHg (confirmed by triplicate measurement at the Study Center), or if the subject is symptomatic (i.e., dizziness, light-headedness, clammy skin, fatigue, blurry vision), the dose will be withheld. Vital signs should be confirmed, and orthostatic hypotension assessment should be performed (See Section 6.1.1.2). In addition, the subject will have home BPM 2 times per day for 1 week. Subject should orally hydrate with 1-liter fluids, including fluids with electrolyte solution (sports drink, etc.). If the subject is symptomatic the Investigator should consider admitting for observation and consider instituting intravenous (IV) hydration with 1-liter normal saline solution and reassess symptoms and orthostatic hypotension assessment. When SBP is $>$ 100 mmHg and is asymptomatic then patient should continue dosing. If the patient has orthostatic vital signs and is asymptomatic, the dose should be withheld until orthostatic hypotension is resolved. The subject will continue to be followed per protocol in the study. Follow-up for subjects that screen fail due to blood pressure inclusion criteria (see Section 5.1) will not be necessary.
2. Prior to Study Day 64 in the Post-Treatment Period or in the Washout Period, should a subject's BPM exceed 170 mmHg (systolic) or 110 mmHg (diastolic) a second measurement must be done within a 30-minute period. If the subject's BP is $>$ 170 mmHg (systolic) or $>$ 110 mmHg (diastolic) within the 30-minute period, an additional BP measurement should be taken within 48 hours at the Study Center, regardless of whether the initial BP measurements were taken in clinic or at home. If the subject then experiences an additional BP measurement $>$ 170 mmHg (systolic) or $>$ 110 mmHg (diastolic) (confirmed by triplicate measurement at the Study Center), they will then be withdrawn from further blinded, randomized treatment. The subject's pre-study antihypertensive medication(s) may be added back per Investigator and Sponsor Medical Monitor judgement. The subject will continue to be followed per protocol in the study. Follow-up for subjects that screen fail due to blood pressure inclusion criteria (see Section 5.1) will not be necessary.
3. On or after Study Day 64 in the Post-Treatment Period, should a subject's BPM exceed 140 mmHg (systolic) or 90 mmHg (diastolic) a second measurement must be done within a 30-minute period. If the subject's BP is $>$ 140 mmHg (systolic) or $>$ 90 mmHg (diastolic) within the 30-minute period, an additional BP measurement should be taken within 48 hours at the Study Center, regardless of whether the initial BP measurements were taken in clinic or at home. If the subject then experiences an additional BP measurement $>$ 140 mmHg (systolic) or $>$ 90 mmHg (diastolic) (confirmed by triplicate measurement at the Study Center), the subject's pre-study antihypertensive medication(s) may be added back per Investigator and Sponsor Medical Monitor judgement. The subject will continue to be followed per protocol in the study.

8.5.4. Safety Monitoring Rules for Platelet Count Results

Platelet count will be monitored at least every week during the Treatment Period and for the first 4 weeks after discontinuation of treatment. The Investigator should review all platelet count results within 48 hours of receipt. If a patient's platelet count falls to $100,000/\text{mm}^3$ or less, then the patient's platelet counts should be monitored weekly. In case of platelet reduction to below $75,000/\text{mm}^3$, the platelet monitoring rule defined in Stopping rules (Section 8.6.3) should be followed.

Any unreportable platelet count result must be rechecked and determined not to have met a stopping rule before dosing can continue.

In the event of a platelet count $< 75,000/\text{mm}^3$, additional laboratory investigations should be conducted (Table 5).

Table 5: Additional Labs to be Performed in the Event of a Platelet Count < 75,000/mm³

To Be Performed at Local Lab
Peripheral smear (should be performed locally, fixed and sent to central lab for review)
Fibrinogen split products or D-dimer on fresh blood
To Be Performed at Central Lab
Citrated sample for platelets
Coagulation panel (PT/INR, aPTT)
CBC with reticulocytes and mean platelet volume (MPV)
Serum B12 and folate
Fibrinogen
von Willebrand factor
Total globulins, total IgA, IgG and IgM
Complement: total C3, total C4, Bb, C5a
hsCRP
Serology for:
HBV, HCV, HIV (if not done for screening)
Rubella
CMV
EBV
Parvo B19
Helicobacter pylori (IgG serum test)
Auto-antibody screen:
Antiphospholipid
Rheumatoid factor
Anti-dsDNA
Anti-thyroid
To Be Performed at Specialty Lab(s)
Antiplatelet antibodies and Anti-PF4 assay
Anti-ASO antibody

Note: The above labs may change as additional data is assessed, and sites will be updated regarding any changes.

8.5.5. Safety Monitoring for Minor Bleeding Events

Minor bleeding events are those that do not fulfill the criteria for major bleeding or clinically-relevant, non-major bleeding events (which are defined in Section 8.6.3), for example excess bruising, petechiae, gingival bleeding on brushing teeth. If a minor bleeding event

occurs, additional testing of coagulation parameters (aPTT, PT, INR) and platelet count should be performed.

8.6. Stopping Rules

For the purposes of the stopping rules, Baseline is defined as:

- Temporary stopping rules for renal function tests – Baseline is defined as the last non-missing measurement prior to the first dose
- Stopping rules for platelets – Baseline is defined as the defined as the last non-missing measurement prior to the first dose

8.6.1. Stopping Rules for Liver Chemistry Elevations

In the event of laboratory results meeting the following criteria, **and the event is without an alternative explanation as discussed with the Sponsor Medical Monitor**, dosing of a subject with Study Drug (ISIS 757456 or placebo) will be stopped permanently; values that are not confirmed due failure to retest or missing lab values will be presumed confirmed:

1. ALT or AST > 8 x ULN, which is confirmed
2. ALT or AST > 5 x ULN, which is confirmed and persists for ≥ 2 weeks
3. ALT or AST > 3 x ULN, which is confirmed **and** total bilirubin > 2 x ULN or INR > 1.5
4. ALT or AST > 3 x ULN which is confirmed, **and** the new appearance (i.e., onset coincides with the changes in hepatic enzymes) of fatigue, nausea, vomiting, right upper quadrant pain or tenderness, fever, rash, and/or concomitant eosinophilia (> ULN)

8.6.2. Stopping Rules for Renal Function Test Results

In the event of laboratory results for either of the following criteria, dosing of a subject with Study Drug (ISIS 757456 or placebo) will be stopped permanently:

1. Confirmed serum creatinine increase that is both ≥ 0.3 mg/dL (26.5 μ mol/L) and $\geq 40\%$ above Baseline creatinine values (refer to Definition of Baseline in Section 8.6)
2. Confirmed 30% decline in eGFR from Baseline eGFR values
3. Confirmed proteinuria (UPCR ≥ 500 mg/g)

The follow-up schedule for any events meeting either of these stopping criteria will be determined by the Investigator **in consultation with** the Sponsor Medical Monitor or designee. At the discretion of the Investigator, a decision to hold or permanently stop study drug may be made based on lesser changes in these parameters observed in isolation or in association with other renal-related abnormalities.

8.6.3. Stopping Rule for Platelet Count Results

In the event of any platelet count less than 75,000/mm³, monitoring frequency and dosing should be adjusted as recommended in the table below.

Table 6: Actions in Patients with Low Platelet Count

Confirmed Platelet Count	Dosing	AESI?	Monitoring
$\geq 75,000/\text{mm}^3$	Yes	No	
 Monitor weekly
$< 75,000/\text{mm}^3$ to $50,000/\text{mm}^3$, in the absence of major bleeding or clinically-relevant non-major bleeding (defined below)	Pause	No	
 Monitor at least twice per week until 3 successive values above $75,000/\text{mm}^3$. Then monitor weekly until values normalize. The suitability of the patient for continued dosing will be determined by the Investigator in consultation with the Study Medical Monitor and will be based on factors such as the original rate of decline in the patient's platelet count, whether any bleeding events were experienced, and the speed of recovery of platelet count after interruption of dosing. The patient must have 3 successive values above $100,000/\text{mm}^3$ before continued dosing is considered. Perform additional labs in Table 5
$< 50,000/\text{mm}^3$ to $25,000/\text{mm}^3$	Permanently Discontinue	Yes, if only accompanied by a major bleeding event or CRNMB event, subject to 15-day expedited reporting	
 Monitor at least twice per week until 3 successive values above $75,000/\text{mm}^3$. Then monitor weekly until values normalize. A hematologist consultation may be considered at the discretion of the Investigator and Study Medical Monitor Perform additional labs in Table 5
$< 25,000/\text{mm}^3$	Permanently Discontinue	Yes, subject to 15-day expedited reporting	
 Monitor daily until 2 successive values above $25,000/\text{mm}^3$. Then monitor twice per week until 3 successive values above $75,000/\text{mm}^3$. Then monitor weekly until values normalize. Administration of steroids* and a hematologist consultation is recommended Perform additional labs in Table 5
$< 10,000/\text{mm}^3$	Permanently Discontinue	Yes, subject to 15-day expedited reporting	
 Monitor daily until 2 successive values above $25,000/\text{mm}^3$. Then monitor twice per week until 3 successive values above $75,000/\text{mm}^3$. Then monitor weekly until values normalize. Hospitalize patient and expedite a hematologist consultation. Administer platelet transfusions and steroids*, if deemed necessary. Perform additional labs in Table 5

* Treatment guidelines for immune thrombocytopenia (Provan et al. 2010) recommend Dexamethasone 40 mg daily for 4 days every 2-4 weeks for 1-4 cycles; Prednis(ol)one 0.5-2 mg/kg/d for 2-4 weeks then taper; or methylprednisolone 30 mg/kg/day for 7 days. (Note: Patient may require continuation with oral steroids after methylprednisolone).

Definition of Major Bleeding Events (Schulman and Kearon 2005):

1. Fatal bleeding, and/or
2. Symptomatic bleeding in a critical area or organ, such as intracranial, intraspinal, intraocular, retroperitoneal, intraarterial or pericardial, or intramuscular with compartment syndrome
3. Clinically overt bleeding leading to transfusion of ≥ 2 units of packed red blood cells or whole blood or a fall in hemoglobin of 2.0 mg/dL (1.24 mmol/L) or more within 24 hours

Definition of Clinically-Relevant Non-Major Bleeding Events

Clinically-relevant non-major bleeding (CRNMB) is defined as overt bleeding not meeting the criteria for major bleeding but that resulted, for example, in medical examination, intervention, or had clinical consequences for a subject.

Definition of Minor Bleeding Events

Minor bleeding events are those that do not fulfill the criteria for major bleeding or clinically-relevant, non-major bleeding events (defined above), for example excess bruising, petechiae, gingival bleeding on brushing teeth.

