9.3.4. Adverse Event of Special Interest

For the purpose of this study, severe reductions in platelet count $< 50,000/\text{mm}^3$ accompanied by a major bleeding (MB) event or clinically-relevant non-major bleeding (CRNMB) event, or platelet count of $< 25,000/\text{mm}^3$ independent of a MB or CRNMB event are considered as AEs of special interest and should be subject to 15-day expedited reporting by the Sponsor to the regulatory agencies.

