Appendix D Grading Scale for Adverse Events Relating to Laboratory Abnormalities

The following grading recommendations for adverse events relating to lab test abnormalities and adverse events at the injection site are based upon the Common Terminology Criteria for Adverse Events (CTCAE) Version 5.0, November 2017.

Adverse Event	Mild	Moderate	Severe
Hematology			
aPTT prolonged	>ULN - 1.5 x ULN	>1.5 - 2.5 x ULN	>2.5 x ULN; bleeding
Eosinophils increased ¹	>ULN and >Baseline	-	Steroids Initiated
Fibrinogen decreased	<1.0 - 0.75 x LLN; if abnormal, <25% decrease from baseline	<0.75 - 0.5 x LLN; if abnormal, 25 - <50% decrease from baseline	<0.5 x LLN; if abnormal, ≥50% decrease from baseline
Hemoglobin decreased (Anemia)	Hemoglobin (Hgb) <LLN - 10.0 g/dL; <LLN - 6.2 mmol/L; <LLN - 100 g/L	Hgb <10.0 - 8.0 g/dL; <6.2 - 4.9 mmol/L; <100 - 80g/L	Hgb <8.0 g/dL; <4.9 mmol/L; <80 g/L; transfusion indicated
Hemoglobin increased**	Increase in >0 - 2 g/dL above ULN or above baseline if baseline is above ULN	Increase in >2 - 4 g/dL above ULN or above baseline if baseline is above ULN	Increase in >4 g/dL above ULN or above baseline if baseline is above ULN
INR increased	>1.2 - 1.5; >1 - 1.5 times above baseline if on anticoagulation	>1.5 - 2.5; >1.5 - 2.5 x baseline if on anticoagulation; monitoring only indicated	>2.5; >2.5 x baseline if on anticoagulation; dose adjustment indicated
Lymphocyte count decreased	<LLN - 800/mm ³ ; <LLN - 0.8 x 10 ⁹ /L	<800 - 500/mm ³ ; <0.8 - 0.5 x 10 ⁹ /L	<500 /mm ³ ; <0.5 x 10 ⁹ /L
Lymphocyte count increased	-	>4000/mm ³ - 20,000/mm ³	>20,000/mm ³
Neutrophil count decreased	<LLN - 1500/mm ³ ; <LLN - 1.5 x 10 ⁹ /L	<1500 - 1000/mm ³ ; <1.5 - 1.0 x 10 ⁹ /L	<1000/mm ³ ; <1.0 x 10 ⁹ /L
Platelet count decreased	<LLN - 75,000/mm ³ ; <LLN - 75.0 x 10 ⁹ /L	<75,000 - 50,000/mm ³ ; <75.0 - 50.0 x 10 ⁹ /L	<50,000/mm ³ ; <50.0 x 10 ⁹ /L
White blood cell decreased	<LLN - 3000/mm ³ ; <LLN - 3.0 x 10 ⁹ /L	<3000 - 2000/mm ³ ; <3.0 - 2.0 x 10 ⁹ /L	<2000/mm ³ ; <2.0 x 10 ⁹ /L
Chemistry			
Acidosis	pH <normal, but ≥7.3	-	pH <7.3
Alanine aminotransferase increased	>ULN - 3.0 x ULN if baseline normal 1.5 - 3.0 x baseline if baseline abnormal	>3.0 - 5.0 x ULN if baseline normal >3.0 - 5.0 x baseline if baseline abnormal	>5.0 x ULN if baseline normal >5.0 x baseline if baseline abnormal

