3.7.2.3 AE of special interest (AESI): Platelet reduction

Per protocol, severe reductions in platelet count $< 50,000/\text{mm}^3$ accompanied by a major bleeding (MB) event or clinically-relevant non-major bleeding (CRNMB) event, or platelet count of $< 25,000/\text{mm}^3$ independent of a MB or CRNMB event are considered as AESI. The AEs meeting the AESI criteria will be captured in the AE CRF page with a check box to indicate. AESI will be summarized by preferred term.

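### The hemoglobin fall that defines a major bleed is printed in mg/dL; its own mmol/L value and Appendix D show that g/dL is meant

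*Combined protocol and SAP*

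**What the plan says.** Protocol Section 8.6.3 defines major bleeding below Table 6. Item 3 covers clinically overt bleeding that leads either to transfusion of at least 2 units or to "a fall in hemoglobin of 2.0 mg/dL (1.24 mmol/L) or more within 24 hours".

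Appendix D grades low hemoglobin on a different scale of units. The mild grade is "Hemoglobin (Hgb) <LLN - 10.0 g/dL; <LLN - 6.2 mmol/L" and the moderate grade is "Hgb <10.0 - 8.0 g/dL; <6.2 - 4.9 mmol/L". The same rows add g/L, and the row for raised hemoglobin uses g/dL. Hemoglobin is not given in mg/dL anywhere in that appendix.

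The definition is used in three places:

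- **Table 6, platelets 25,000 to below 50,000/mm³.** The AESI column reads "Yes, if only accompanied by a major bleeding event or CRNMB event, subject to 15-day expedited reporting".
- **Table 6, platelets 50,000 to below 75,000/mm³.** The row that pauses dosing applies only if there is neither major nor clinically relevant non-major bleeding (CRNMB).
- **Section 9.3.4.** A count below 50,000/mm³ is an AESI when "accompanied by a major bleeding (MB) event or clinically-relevant non-major bleeding (CRNMB) event".

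SAP Section 3.7.2.3 repeats the AESI rule without restating the hemoglobin threshold. On data capture it says: "The AEs meeting the AESI criteria will be captured in the AE CRF page with a check box to indicate".

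**The concern.** One threshold is printed in two units, and the two values cannot both hold. A fall of 2.0 mg/dL in hemoglobin is far below anything a laboratory reports, whereas 1.24 mmol/L is a substantial fall.

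An investigator who applies the mg/dL figure would class an overt bleed as major after any measurable drop within 24 hours. The line between major and lesser bleeding would then disappear wherever two such hemoglobin values exist. What is at stake is the classification of bleeds, the AESI flag with its expedited report to regulators, and whether the pause row in Table 6 applies.

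**Working it through.** **Inputs**

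- Printed threshold (Section 8.6.3, item 3): 2.0 mg/dL, given as equal to 1.24 mmol/L.
- Appendix D, pair 1: 10.0 g/dL and 6.2 mmol/L.
- Appendix D, pair 2: 8.0 g/dL and 4.9 mmol/L.

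**Step 1: the protocol's own conversion factor (mmol/L per g/dL)**

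- Pair 1: 6.2 / 10.0 = 0.620.
- Pair 2: 4.9 / 8.0 = 0.6125.

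**Step 2: convert the printed 2.0 mg/dL**

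- 2.0 mg/dL = 0.002 g/dL.
- Pair 1: 0.002 × 0.620 = 0.00124 mmol/L.
- Pair 2: 0.002 × 0.6125 = 0.001225 mmol/L.
- The printed 1.24 mmol/L is not reproduced. It is 1.24 / 0.00124 = 1000 times larger (1.24 / 0.001225 = 1012 times with pair 2).

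**Step 3: convert 1.24 mmol/L back**

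- Pair 1: 1.24 / 0.620 = 2.00 g/dL.
- Pair 2: 1.24 / 0.6125 = 2.02 g/dL.

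With g/dL in place of mg/dL, pair 1 returns the printed value exactly: 2.0 × 0.620 = 1.24. Pair 2 gives 2.0 × 0.6125 = 1.225 mmol/L, about 1.2% lower, which the rounding of 4.9 explains (4.95 / 8.0 = 0.61875, and 2.0 × 0.61875 = 1.2375). So the number 2.0 and the mmol/L value are both sound, and only the unit is wrong.

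**Step 4: size of the literal threshold**

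The documents do not state the laboratory's reporting precision. Appendix D's one-decimal g/dL limits suggest steps of 0.1 g/dL, which is an assumption.

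- Steps of 0.1 g/dL: 0.002 / 0.1 = 1/50 of a step.
- Steps of 0.01 g/dL: 0.002 / 0.01 = 1/5 of a step.

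On either assumption, the smallest fall that can be recorded exceeds the literal threshold.

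**Step 5: where a misclassification could change an action**

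| Platelets (/mm³) | Effect of wrongly calling a minor bleed major |
|---|---|
| 50,000 to <75,000 | Subject falls outside the pause row's no-bleeding condition |
| 25,000 to <50,000 | Becomes an AESI with 15-day reporting; dosing stops in any case |
| <25,000 | None: AESI and permanent discontinuation apply in any case |

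If the bleed already qualifies as CRNMB, nothing changes in any row, because CRNMB triggers the same conditions.

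**Step 6: would a 24-hour pair of hemoglobin values exist?**

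The shortest gap between scheduled hematology samples in Appendix A is Day 1 to Day 3, so the schedule supplies no such pair. For minor bleeds, Section 8.5.5 says "additional testing of coagulation parameters (aPTT, PT, INR) and platelet count should be performed". Appendix B lists hemoglobin with platelets under hematology, so that extra sample could yield a hemoglobin value. Table 5 also asks for a blood count below 75,000/mm³. Neither provision requires a repeat within 24 hours.

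**The case against.** The printed unit itself cannot be defended. The case on the other side is that the error has almost no practical effect.

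- **The correct value stands beside the wrong one.** A reader who uses 1.24 mmol/L, or who knows that hemoglobin is reported in g/dL, will apply the intended threshold. Nothing in the documents shows that a site would use 0.002 g/dL. This stands, but a definition that feeds expedited reporting should not rely on readers noticing a contradiction.
- **CRNMB absorbs most cases.** Its definition includes overt bleeding that led to a medical examination, so a subject bled twice within 24 hours may already qualify. This largely stands. A few cases remain, because Section 8.5.5 prescribes testing for bleeds that stay minor.
- **The needed data are rarely collected.** In the one band where AESI status can change, Table 6 asks for counts at least twice a week. Daily counts begin only below 25,000/mm³, where bleeding no longer affects AESI status. This stands.
- **The pause-row effect leads nowhere definite.** Table 6 has no row for 50,000 to below 75,000/mm³ with major bleeding or CRNMB. That is a gap with either unit. The wrong unit would only send more subjects into it.
- **No analysis program uses the threshold.** The SAP takes AESIs from a check box and describes no derivation from hemoglobin. This is true, but the tick then depends on how the investigator reads the definition.

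These points limit the consequence and leave the error in place.

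**Conclusion.** The unit in item 3 is wrong. On the protocol's own conversion, 1.24 mmol/L is 2.00 to 2.02 g/dL, and the printed 2.0 mg/dL is too small by a factor of 1000. This conclusion needs nothing beyond Section 8.6.3 and Appendix D. Only the comparison with laboratory reporting steps rests on an assumption, and it holds at both 0.1 and 0.01 g/dL.

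The severity is minor. AESI status could change only for an otherwise minor bleed at 25,000 to below 50,000/mm³ with two hemoglobin values within 24 hours. The error acts in one direction, towards more reports. Sample size, type I error and the efficacy analyses are unaffected.

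**What to change.** In protocol Section 8.6.3, Definition of Major Bleeding Events, item 3, replace mg/dL with g/dL, so that the threshold is 2.0 g/dL (1.24 mmol/L). The SAP needs no change because it does not restate the threshold. The cost is a one-unit protocol correction, with no effect on patients, data or analysis.
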